**APPENDIX B. SIGNS AND SYMPTOMS OF HYPERTHYROIDISM**

This table includes an overview of the most common symptoms and signs for the diagnosis of hyperthyroidism. The presence of several of the following signs/symptoms may be indicative of hyperthyroidism and should be further investigated.

**Table 9: Signs/Symptoms of Indicative of Hyperthyroidism**

Heat intolerance
Hyperkinesis
Atrial fibrillation
Excessive sweating
Increased Appetite
Decreased Weight
Casual heart rate/pulse >90 bpm
Palpitations
Tiredness
Nervousness
Hot hands
Shortness of breath
Moist hands
Tremor
Increased frequency of bowel movements
Urinary frequency and nocturia

[figure not shown]
**APPENDIX C. INJECTION SITE DISCOMFORT ASSESSMENT****Numeric Rating Scale for Injection Site Discomfort**

**Investigative Site Instructions:** The subject should complete the 11-point NRS for Injection Site Discomfort at 10 ( $\pm 2$ ) minutes after injection of study drug. The subject will complete the NRS by drawing a circle around the number corresponding to the perceived intensity (severity) of discomfort according to the instructions below. The goal is for the subject to report the amount of discomfort, if any, remaining at each timepoint, as opposed to reporting the transient pain associated with needle insertion.

**Note:** If a subject is unable to physically complete the questionnaire, the subject will indicate the number on the NRS corresponding to their level of discomfort, and study staff will circle it. Documentation will be provided on each completed questionnaire as to who completed the form.

**Subject Instructions:** Ignoring any pain from insertion of the needle, please draw a circle around the number on the scale below that corresponds to the intensity (severity) of any discomfort you are feeling right now at the study drug injection site.

For example, if you are currently feeling no discomfort, you should circle the number “0” on the left end of scale. If you are currently feeling the worst discomfort possible, you should circle number “10” on the right end of the scale.

Source: [Downie et al, 1978](#)

**Injection Site Discomfort Description and Duration Questionnaire**

**Study Personnel Instructions:** Question 1 should be completed by the subject at 10 ( $\pm 2$ ) minutes after study drug injection. If the answer to Question 1 is ‘Yes’ then complete the following:

- Questions 1a and 1b should be assessed at 10 ( $\pm 2$ ) minutes after study drug injection and,
- Question 1c only should be assessed once discomfort has fully resolved.

If the answer to Question 1 is ‘No’, then questions 1a, 1b, and 1c should not be assessed.

The goal is for the subject to report if they had any discomfort and if there was discomfort, the qualitative nature and duration of discomfort associated with the delivery of study drug, ignoring any transient pain associated with injection of study drug.

**Note:** If a subject is unable to physically complete the questionnaire, the subject will provide verbal responses, which will be recorded on the questionnaire by study staff. Documentation will be provided on each completed questionnaire as to who completed the form.

**Subject Instructions:** Please answer the questions below.

1. Did you have any discomfort from the study drug administration?

Yes  No

If yes,

1a. How would you describe any discomfort you felt from the study drug? (Check **all** that apply):

Pain (e.g., throbbing, soreness, muscle ache)

Itching

Tingling, twitching or numbness

Irritation (e.g., burning, stinging)

Other (specify): \_\_\_\_\_

1b. About how long after the study drug administration did the discomfort start?

(Please enter a number) \_\_\_\_\_ minutes

1c. In total, how long did the discomfort last? (Please enter a number): \_\_\_\_\_ minutes

Source: [Downie et al, 1978](#)

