## 13.5. Study Endpoints

### 13.5.1. Primary Endpoints

- Safety endpoints collectively include incidence, frequency, severity, and relationship to study drug of TEAEs, including clinically significant vital sign measurements, safety laboratory test results, ECGs, and physical examinations
- Tolerability assessments include Modified Draize Scale and Injection Site Discomfort questionnaires
- Geometric mean ratio of the weekly dose of XP-8121 SC (in  $\mu\text{g}$ ) to the daily dose of oral levothyroxine (aka dose conversion factor), where the XP-8121 dose corresponds to the administration immediately preceding collection of blood TSH used to determine normalization at the end of Maintenance Period

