### 13.7.4. Local Tolerability

Local tolerability (incidence of injection site discomfort and erythema/edema) will be summarized by protocol-specified timepoint following SC injections of XP-8121. Specifically, subjective injection site discomfort as reported by the NRS and Discomfort Description and Duration Questionnaire will serve as the data basis. The incidence of any injection site discomfort (score  $>0$  on the ordinal rating scale) will be analyzed descriptively. Descriptive statistics also will be provided for time of onset and duration (of discomfort), and discomfort description (i.e., pain, irritation, itching, etc.).

In addition, erythema and/or edema formation at the injection site will be assessed using the Modified Draize Scale. Counts and percentages of each category on the erythema/edema spectrum will be presented for each scheduled timepoint.

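### The two Appendix C discomfort forms set aside different kinds of pain, so brief drug-caused discomfort may be described and timed inconsistently

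*Protocol*

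**What the plan says.** Protocol section 13.5.1 lists tolerability among the primary endpoints: "Tolerability assessments include Modified Draize Scale and Injection Site Discomfort questionnaires". Appendix C contains the two discomfort forms, and sections 11.2 and 11.3 require both 10 (±2) minutes after each injection.

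- **NRS.** Staff are told that the aim is to rate remaining discomfort "as opposed to reporting the transient pain associated with needle insertion". The subject's own instruction likewise sets aside pain from the needle going in.
- **Questionnaire.** Staff are told that the aim is to learn of any discomfort and, if there was some, its nature and the "duration of discomfort associated with the delivery of study drug, ignoring any transient pain associated with injection of study drug". The subject's instruction only asks for the questions to be answered. Question 1 reads "Did you have any discomfort from the study drug administration". Question 1a offers, among other options, "Irritation (e.g., burning, stinging". Questions 1b and 1c ask for time to onset and total duration in minutes. If the answer to Question 1 is no, 1a to 1c are not asked.

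On analysis, section 13.7.4 bases local tolerability on both forms and adds: "Descriptive statistics also will be provided for time of onset and duration (of discomfort), and discomfort description". SAP section 6.9.7 takes onset and duration as they stand on the eCRF. SAP section 9.8.7 summarizes them by timepoint, with counts and percentages for the description of discomfort.

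**The concern.** Injecting the drug is how it is delivered. An instruction to record discomfort from delivery while ignoring transient pain from injection can therefore be taken to cancel itself for short-lived events. Stinging or burning on injection is an obvious local effect to look for with a DMSO-containing subcutaneous solution, and it is also the effect most likely to be called transient. Neither document defines that word.

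At stake is whether the description, onset and duration data mean the same thing for every subject and site. A subject guided by staff who apply their instruction may leave out brief drug pain. A subject who answers unaided sees no exclusion and may report needle pain. If brief drug pain is left out, its description and onset are lost as well, and the remaining durations lean towards longer events. The SAP takes the values as recorded, so the analysis cannot repair this.

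**Working it through.** The plan attaches no figure to this point, so the check is a comparison of texts.

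**Step 1. What each form excludes, and when it asks.**

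| | NRS | Questionnaire |
|---|---|---|
| Exclusion told to staff | Needle-insertion pain | Transient pain from injection of the drug |
| Exclusion told to the subject | Needle-insertion pain | None |
| When completed | 10 (±2) minutes | 10 (±2) minutes; 1c once discomfort has resolved |
| Period covered | The moment of rating | Since the injection (Question 1 is in the past tense) |

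The NRS is consistent between staff and subject. The questionnaire differs from the NRS, and its staff text differs from its subject text.

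**Step 2. Is the questionnaire consistent with itself?** On the literal reading it is not. The staff sentence asks for "the qualitative nature and duration of discomfort associated with the delivery of study drug" and then drops the brief part of it. Question 1 has no lower limit on how long discomfort must last. Question 1a lists burning and stinging as reportable.

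**Step 3. Can another local tolerability form fill the gap?** The NRS cannot record pain that has resolved before 10 (±2) minutes, because it rates only current discomfort. That would be so whatever its exclusion said. The Modified Draize Scale, at 30 (±5) minutes, grades erythema and edema, not pain. Only the questionnaire can record resolved discomfort, and its staff instruction is the one with the wider exclusion.

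**Step 4. Which summaries are exposed?**

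- *Description, onset and duration (1a, 1b, 1c):* exposed. They come only from the questionnaire and depend on the answer to Question 1.
- *Incidence of any discomfort:* not exposed. Protocol section 13.7.4 defines it as a score above 0 on the rating scale, which is the NRS.
- *Intensity categories:* not exposed. SAP section 6.9.7 assigns them by score bands that match the 11-point NRS.
- *A yes/no summary of Question 1:* not listed in SAP section 9.8.7.
- *Dose conversion factor, sample size and power:* not exposed. None of them uses these data, and Protocol section 13.7 states that no hypotheses are tested on safety data.

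**The case against.** There are four fair counter-arguments.

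1. **The phrase may mean the needle stick.** Transient pain from injection can be read as the act of injecting, as distinct from discomfort caused by the drug delivered. The NRS wording supports this, and on that reading the sentence does not contradict itself. This stands as a possible reading, so the wording is ambiguous and is not a demonstrated exclusion of a drug effect. It also supports the edit: if needle pain was meant, the NRS already says so plainly.

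2. **The subject never sees the exclusion.** It appears only in the staff instruction, as a statement of the goal, and nothing tells staff to pass it on. Staff write on the form only when a subject cannot physically complete it, and then they record the subject's verbal responses. A reader might infer that brief drug-caused pain drops out of the endpoint. The documents do not support that, because the subject answers an unrestricted question and such pain can still be recorded. What remains is a risk that depends on how staff use their instruction.

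3. **Incidence is not touched.** A reader might infer that the reported incidence of discomfort is biased towards good tolerability. Step 4 shows that it is not, since incidence comes from the NRS. The NRS can miss pain that has resolved by 10 minutes, but the cause is its timing, and the edit proposed here does not change that.

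4. **Adverse event reporting is a second route.** Protocol section 12.3 collects adverse events from spontaneous report, open questions and observation, and injection site reaction was reported in Study XP-8121-101. This stands as a safeguard. It does not feed the description, onset and duration summaries, for which section 13.7.4 names the NRS and the questionnaire as the source.

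**Conclusion.** The concern holds in a limited form. The two discomfort forms carry different exclusions. The questionnaire's staff text, read literally, conflicts with its own goal, with Question 1 and with Question 1a. This creates a risk of under-reported or inconsistent description, onset and duration of discomfort, all of them descriptive summaries within a listed primary tolerability endpoint.

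The size of the risk is unknown. One could multiply the number of injections by an assumed rate of brief pain, but the documents give neither that rate nor the share of such episodes that staff guidance would turn into a no. Any count would rest wholly on those two assumptions, so none is offered. The direction is not certain either: the staff exclusion can lose brief drug pain, while the missing subject exclusion can let needle pain in.

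The conclusion assumes that at least some staff apply the sentence literally or pass it on to subjects. If none do, the only remaining fault is that the questionnaire's subject text lacks the needle exclusion that the NRS has. The change is still worth making, because only this form can record discomfort that resolved before the NRS rating.

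**What to change.** Make two edits to the Appendix C questionnaire and the printed form:

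1. In the study personnel instructions, change "ignoring any transient pain associated with injection of study drug" so that the pain set aside is that of needle insertion and no longer that of injecting the study drug. This matches the NRS.
2. Print the same needle-only exclusion in the questionnaire's subject instructions, as the NRS already does.

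The cost is one phrase, printed in two places on one form. No visit, assessment or analysis is added, and dosing is unaffected. The downside is that somewhat more brief discomfort may be recorded.

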## APPENDIX D. SUBJECT PREFERENCE SURVEY

**By participating in this study (XP-8121-120), you have now received thyroid replacement therapy in two different ways:**

1. A once-daily oral pill (e.g., Synthroid) that should be taken every day at the same time before breakfast with only water and on an empty stomach and then wait for at least 30 minutes before eating, drinking, or taking any other medications.
2. A once-weekly injectable medication administered under the skin that can be taken at any time of day.

**Please think back to your participation in this study (XP-8121-120) and consider your life and what works best for you. Think about the treatment itself, rather than the doctor's office or study personnel. There are no right or wrong answers.**

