- n: **XP-8121 administration:** The XP-8121 SC initiation dose will correspond to 50% of the target XP-8121 dose, which is calculated as the current daily oral levothyroxine dose multiplied by 4, rounded up to the nearest 50  $\mu$ g. Based on fT4 levels XP-8121 will be titrated biweekly by intervals of 25% of the target dose. See Section 7.4.2 and Section 7.4.3 for further details about dose titration and dose adjustment criteria during the Titration and Maintenance Periods, respectively. The time of weekly (every 7 days) XP-8121 SC dose administration will remain consistent throughout the study and will occur within  $\pm 2$  hours of the time of the XP-8121 SC initiation dose (Section 10.5).
- o: A subgroup of subjects (~12), who have been on Synthroid for at least 3 months prior to Screening and who have maintained adequate trough T4 (free and total) levels in the Maintenance Period will participate in a PK substudy. The study reference ranges for T4 (free and total) and TSH are: 0.78 to 1.42 ng/dL (fT4), 5.53 to 10.96  $\mu$ g/dL (total T4), and 0.47 to 4.68  $\mu$ IU/mL (TSH). During Week 4 of the Maintenance Period, subjects will be housed in the CRU for 9 days and 8 nights to undergo PK sample collections at specified timepoints as outlined in [Table 5](#). Subjects will be admitted to the CRU on Maintenance Day 21 (day prior to XP-8121 administration and initiation of PK sampling) and discharged from the CRU on Maintenance Day 29 (168 hr PK sample).
- p: **Modified Draize Scale:** Injection site erythema and edema will be assessed using Modified Draize Scales 30 ( $\pm 5$ ) minutes after injection of XP-8121. If the Draize score is  $>1$  at 30 minutes, the subject will be discharged, and a follow up visit will be scheduled at 24 ( $\pm 3$ ) hr post-dose to allow the Investigator or designee to complete an assessment of the injection site using the Modified Draize Scale.
- q: **Injection Site Discomfort evaluations:** Injection site discomfort will be assessed at 10 ( $\pm 2$ ) minutes after injection of XP-8121 using the Numeric Rating Scale for Injection Discomfort, and subjects will complete a Site Discomfort Description and Duration Questionnaire 10 ( $\pm 2$ ) minutes after injection.
- r: **Subject Preference Survey:** Survey will be completed during the End of Maintenance Visit or Early Termination Visit.

Protocol XP-8121-120

XP-8121 (levothyroxine sodium) injection

---

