#### 6.1.3. Exploratory Objectives

- To characterize the dynamics of thyroid hormones and TSH in blood during and after titration (ie, Titration and Maintenance Periods) with XP-8121
- To characterize the PK of plasma thyroid hormones following multiple once-weekly XP-8121 SC injections in adult subjects with hypothyroidism
- To compare patient treatment satisfaction between daily oral levothyroxine and once-weekly XP-8121 SC injections

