### 9.3. Treatment Compliance

All doses of XP-8121 will be administered at the CRU. Study drug administration during Titration and Maintenance Periods will be recorded on the drug accountability log.

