## 10.5. Administration and Dose

Subjects will receive single doses of XP-8121 on a weekly basis (every 7 days). The time of the weekly XP-8121 dose administration will remain consistent throughout the study and will occur within  $\pm 2$  hours of the time of the XP-8121 SC initiation dose. The SC injections of the XP-8121 will be performed within the perumbilical region of the abdomen.

The Investigator and/or delegate is responsible for the education of study staff as to the correct timing and procedure for administration of the study drug. Further details are provided in the Pharmacy Manual.

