## **21. APPENDICES**

## APPENDIX A. TITRATION ALGORITHM

- a. Corresponds to 50% of the target weekly dose of XP-8121 (in  $\mu$ g), which is calculated as the current daily oral levothyroxine dose (in  $\mu$ g) multiplied by 4 rounded up to the nearest 50  $\mu$ g.
- b. During the Titration Period, XP-8121 will be titrated based on individual response to therapy (using blood free T4 [fT4] trough concentration as a fast-response, interim biomarker of replacement adequacy) at intervals no more frequent than every other week and in dosage increments corresponding to 25% of the target dose, up to a maximum of 125% of the target dose or 1500  $\mu$ g (whichever is lower).
- c. If a drug-related adverse event is reported or if overdosage is a concern, the Investigator should consult with the Medical Monitor before up-titrating.
- d. Dosing titration decisions should be made after conferring with the Medical Monitor.
- e. Once subjects have completed the Titration Period they will continue at the same dose and time of administration of XP-8121 in the Maintenance Period.

**Note:** Subjects not achieving an adequate fT4 at  $\leq 125\%$  of the target dose or the maximum weekly dose of 1500  $\mu$ g may also continue into the Maintenance Period at the discretion of the Investigator and after conferring with the Medical Monitor.

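### The Subject Preference Survey introduces the pill by its restrictions and the injection by one advantage the trial did not test, so a descriptive exploratory result leans towards XP-8121 by an unknown amount

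*Protocol*

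**What the plan says.** Protocol Appendix D opens by telling subjects that they have now had thyroid replacement in two ways, and describes each.

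- Pill: a daily tablet "that should be taken every day at the same time before breakfast with only water and on an empty stomach", followed by a wait of at least 30 minutes before food, drink or other medicines.
- Injection: "A once-weekly injectable medication administered under the skin that can be taken at any time of day".

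The form then asks subjects to think back over the study, to judge the treatment itself and not the clinic or its staff, and to regard no answer as right or wrong. Three questions follow: which treatment they would choose (pill, injection or no preference), how strong the preference is, and the reasons for it.

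The dosing rule is in Protocol Section 10.5: "The time of the weekly XP-8121 dose administration will remain consistent throughout the study and will occur within" 2 hours, either way, of the time of the initiation dose. Table 2 footnote n repeats it. Appendix A adds that after titration "they will continue at the same dose and time of administration of XP-8121 in the Maintenance Period". Section 9.3 states: "All doses of XP-8121 will be administered at the CRU".

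The survey belongs with the exploratory objective "To compare patient treatment satisfaction between daily oral levothyroxine and once-weekly XP-8121 SC injections" (Section 6.1.3). It is listed as an exploratory endpoint in Section 13.5.3. Section 13.5.3.1 and SAP Section 9.7 plan only counts and percentages for each answer.

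**The concern.** A preference question should put the options in comparable terms. Here one option comes with a list of inconveniences and the other with a convenience, immediately before the choice is made. The protocol has injection burdens it could have named: it scores discomfort, erythema and edema after every dose.

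The one advantage given to the injection is also something no subject could report from the trial. Doses were tied to a clock time, and no objective or endpoint examines time of dosing.

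What is at stake is how the preference percentage can be read. The study is single-arm and open-label, so neither a control group nor blinding offsets the wording. A majority for the injection could not be separated from the way the question was put.

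**Working it through.** The plan gives no sample size, power, margin or interval for this survey, so there is no stated figure to reproduce. The check is mainly a comparison of texts.

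**1. The two descriptions (Appendix D)**

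| | Pill | Injection |
|---|---|---|
| Frequency | daily | weekly |
| Time of day | fixed, before breakfast | any |
| Food and drink | water only, empty stomach, at least 30 minutes' wait | nothing stated |
| Burdens of the route | not applicable | none stated |

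The pill text broadly agrees with the usual instructions described in Protocol Section 5 (empty stomach, 30 to 60 minutes before food). The fault is therefore not a false statement about the pill. It is the unequal treatment, together with an untested statement about the injection.

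**2. What subjects experienced (Section 10.5, Table 2 footnote n, Appendix A, Section 9.3)**

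- Permitted window after the first dose: 2 + 2 = 4 hours, and 4/24 = 16.7% of the day.
- Doses for a subject who completes: 2 to 8 weekly titration doses plus 4 maintenance doses, so 6 to 12, all at the unit.
- No clock time is set for the first dose. Different subjects could be dosed at different times, but no subject could move the time by more than 2 hours.

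**3. Reach of the problem (Table 2 and footnotes r and s)**

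The TSQM-9 is completed before the first dose and on Maintenance Day 22. The survey comes later, on Day 29 or at early termination. Its wording cannot affect the TSQM-9 answers.

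**4. Illustration only**

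Assume that all 44 subjects answer, that 50% would choose the injection under neutral wording, and that the wording adds 5, 10 or 20 percentage points. The shifts and the 50% are assumptions with no source in the documents. The 95% half-width at 50% is 1.96 × √(0.25/44) = 0.148, or 14.8 points. Exact (Clopper-Pearson) limits are the 2.5% quantile of Beta(x, n − x + 1) and the 97.5% quantile of Beta(x + 1, n − x):

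| Assumed shift | x of 44 | Observed | 95% interval |
|---|---|---|---|
| 0 | 22 | 50.0% | 34.6% to 65.4% |
| 5 points | 24 | 54.5% | 38.8% to 69.6% |
| 10 points | 26 | 59.1% | 43.2% to 73.7% |
| 20 points | 31 | 70.5% | 54.8% to 83.2% |

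Only the largest assumed shift would by itself exclude 50%. The plan calculates no such interval, and with three answer options 50% is only a convenient reference.

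**The case against.** **The dosing rule is not a rule about the product.** A reader might infer that the protocol forbids what the form says. The documents do not support that as a general statement. The 2-hour rule governs trial conduct within a subject after the first dose; the first dose has no set clock time, and Section 10.5 ties dosing to no meal or fast. The phrase on the form can be read as meaning that the injection is not tied to meals. This stands: the accurate criticism is that the flexibility was not tested.

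**The form tells subjects to set the clinic aside and offers a no-preference answer.** Both are real safeguards. They weaken any argument based on dosing at the unit, and they mean the replacement text should not mention clinic staff. Neither balances the two descriptions.

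**Respondents know both treatments.** They had taken oral levothyroxine for at least 3 months, and completers had at least six injections, each followed by discomfort and skin assessments. This probably limits how far the wording can move answers. It does not change the direction in which the wording leans.

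**The stem does not simply supply the reasons.** A reader might infer that it feeds straight into the reasons offered. The next question is about strength of preference; reasons come third. Apart from frequency, the listed reasons are not named in the stem, and all can be chosen for either treatment. That inference should not be drawn.

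**It is one exploratory item.** Correct, and it sets the weight of the point.

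**Conclusion.** The point holds in a limited form. The survey's opening is asymmetric, and it credits the injection with a flexibility that no subject experienced across doses. That it leans towards XP-8121 is a judgement from one-sided wording; the size cannot be estimated from the documents, and the 5 to 20 points used above are assumptions. A reader might infer that a majority for the injection would be produced by the wording. The documents do not support that either: shifts of 5 or 10 points stay within the 14.8-point half-width, and respondents have first-hand experience of both treatments.

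The consequence is confined to the preference percentages. The dose conversion factor, the TSQM-9 comparison, the sample size and the safety conclusions do not depend on this form. The change is worth making because it is cheap and the lean cannot be corrected after collection.

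**What to change.** In Appendix D, replace the two descriptions with neutral, parallel wording that matches the answer options:

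1. *a once-daily oral pill*
2. *a once-weekly injection under the skin*

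Delete both the list of pill restrictions and the statement about time of day. Add nothing about clinic staff: it would be non-parallel and would conflict with the form's instruction to disregard the setting. Leave the three questions as they are.

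If the current form has already been used, keep those responses, report results by form version, and state in the study report that the current stem was asymmetric and described dosing flexibility the study did not test.

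The cost is a one-page form change with IRB notification, and no added visits, samples or tests. The drawback is that about 44 responses may be split between two versions. If they split evenly, the half-width at 50% within each version is 1.96 × √(0.25/22) = 0.209, or 20.9 points. If nearly all responses are already in, the reporting statement alone would be proportionate.
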